Official Title: Use of Dermabond in Mitigation of Spinal Cord Stimulation Trial Lead Migration

NCT05914311

IRB Approval Date: 08/05/2025

Use of Two Standards of Care: Dermabond versus Suture in Mitigation of Spinal Cord Stimulation Trial Lead Migration

Principal Investigator, Co-investigator(s): [name] (PI); ; [name] MD; [name] MD; [name] MD PhD

Sponsor or funding source: Department of Anesthesiology at Atrium-Health Wake Forest Baptist Medical Center

Background, Rationale and Context

Spinal Cord Stimulation is a FDA approved and effective treatment for chronic pain. It is indicated in patients with varying medical conditions ranging from neuropathic pain syndromes to failed back surgery syndrome.¹ A prognostic test (trial) is required prior to the permanent implantation of a Spinal Cord Stimulation (SCS) system. The Spinal Cord stimulator 'trial' (prognostic tests) requires precise placement of SCS leads in the thoracic epidural space to capture the pain areas including the low back and lower extremities.¹ Standard medical practice is to place two SCS leads per patient treated to obtain appropriate neuroanatomical coverage. Since the leads are not anchored into the deep tissue (thoracolumbar fascia), migration of the leads can occur and result in suboptimal trial resulting in a technical failure of the prognostic test increasing the possibility of false negative results. Migration of the SCS leads can result in up to 2.49 mm to 3.24 mm migration in the leads depending on trial length.^{2,3} Early studies on SCS leads placed percutaneously demonstrates migrations rates occurring in 13.2 to 69.2% of cases.^{4,5} During the trial the distal end of the leads are within the thoracic and lumbar epidural space, and the proximal end of the leads are externalized and can be prone to migration. The leads are typically secured in place with tape alone or tape and suture and/or dermabond.

The suture is a silk sterile surgical suture material. Dermabond is a quick drying adhesive that is currently utilized for assisting in the closure of medical incisions with minimal risk. The use of Dermabond has not been formally investigated but is in common use for securing SCS 'trial' leads. It is unknown which standard of care mechanism of securing SCS trials leads is superior in reducing lead migration. One may be more effective alternative to decrease the incidence of such lead migration, thereby allowing for improvement of outcomes during spinal cord stimulation trial lead placement (in anticipation of surgical placement of spinal cord stimulators for the treatment of chronic pain).

Objectives

Main objective

Determine if the use of Dermabond plus suture as compared to suture alone at the insertion site of a trial spinal cord stimulator lead will lead to less lead migration at the end of the trial period (typically 5-8 days).

Additional Objectives

1. Assess if lead migration changes effectiveness of 'trial'
2. Compare patient satisfaction between patients with migration and without

3. Assess trial lengths effects 5 versus 6 versus 7 versus 8 days on lead migrations rates
4. Determine if there is a change in lead position when using Dermabond plus suture vs suture alone when laying prone on the operating table and then standing and having a PA x-ray performed with radiology

Methods and Measures

Design

All patients who are being considered for a permanent spinal cord stimulator placement are required to have spinal cord stimulator 'trial' leads placed to ensure they are an appropriate candidate for treatment with this device. These trial leads are placed by pain medicine physicians in the pain centers and are secured with either tape and suture, or tape and a combination of Dermabond with suture. Security is at the discretion of the inserting physician. Currently it is not known which method is the best method of securing trial leads to prevent lead migration.

Interventions and Interactions

This study will be a controlled trial of the two standard of care methods of securing SCS leads in which the trial leads (left and right) will be secured with 1 lead being secured with a suture only while the 2nd lead will be secured after placement with both a suture in addition to Dermabond. All other factors in the SCS trial lead placement will be unaffected by this study. In this manner, the patient will serve as their own control. This will limit confounding factors between patients that may predispose them to migration based on body habitus, sheer forces of back musculature, and other physical attributes that could augment lead migration. In the standard of care SCS 'trials', one lead is typically place to the left of midline (1-2 cm from midline), and another lead to the right of midline (1-2 cm from midline). Although, the anatomy of the two placement location should be identical, we will randomize which lead (left or right) in each patient gets suture plus Dermabond versus suture only to limit any potential procedural (though unlikely) bias in which SCS lead gets secured in a certain fashion. This is within participant randomization. Demographics of the subject to be retrieved include the following: Age, BMI, height, weight, race, ethnicity, history of spine surgery, sex at birth. We will also collect the radiological information required to meet the study objective of this protocol.

As is the standard of care with this subject population, once procedure is completed on Day 0, the patient will be sent for X-ray imaging right after the trial as well as between days 5-8 post procedure. During this second X-ray, the placement of the leads will be evaluated by measuring the amount of lead migration by a physician not involved in the trial. Lead migration will be measured in millimeters from original placement on X-ray imaging. Of note, imaging is obtained during the placement of the trial leads via fluoroscopy. Depending on the location,

the post trial images may be done via x-ray imaging or via fluoroscopy. Either radiological studies are acceptable methods to be used in the analysis of lead migration for this study. The average and median mm of migration per trial will be compared between the two mechanisms of securing the lead. The rate of migration is defined as greater than 4 mm between the two groups. Patient satisfaction survey will also be reviewed upon lead removal by a member of the study team.

Setting

This will be a single center, academic setting at Atrium Wake Forest Baptist with the Pain Service Line.

Subjects selection criteria

- **Inclusion Criteria**

Any patient presenting to the Pain Service Line for SCS 'trial' lead placement in the thoracic spine defined as terminal tip end in the thoracic spine.

- **Exclusion Criteria**

Allergy to Dermabond and/or Suture material.

Inability to place two leads in the patient.

Lead placement outside of the thoracic spine

- **Sample Size**

Assuming the mean lead migration for use of Dermabond is 2.49 mm compared to mean non-Dermabond usage of 3.24mm, with variance of 1mm, total sample size need for study with study power of 80% with 95%CI for 2-tail test is 56 for both the groups. Lead migration is estimated to occur at a rate of about 13.2% and this number would provide enough analysis to determine if there is a difference in the rates of migration between the groups. No interim analysis will be performed as there is no potential significant harm to the patient and both approaches are standard of care.

Outcome Measure(s)

- **Primary Outcome Measure**

Migration rate of trial leads anchored with Dermabond + suture versus suture alone.

- **Title:** Migration rate of trial leads anchored with Dermabond + suture versus suture alone
- **Description:** Change in 'trial' lead position as measured in millimeters when comparing initial x-ray after placement versus x-ray taken at lead removal 5-8 days after placement.
- **Time Frame:** 5-8 days after placement of trial lead

- **Secondary Outcome Measure**

- **Title:** Number of patients who received pain relief from the SCS 'trial'
- **Description:** Number of responders to the prognostic lead placements defined as >50% pain relief over the length of the trial.
- **Time Frame:** 5-8 Days after placement of trial leads

- **Secondary Outcome Measure**

- **Title:** Patient satisfaction
- **Description:** Lower satisfaction in patients that had lead migration versus patients that did not
- **Time Frame:** 5-8 Days after placement of trial leads

- **Secondary Outcome Measure**

- **Title:** Effect of length of trial on migration
- **Description:** Does a longer trial predispose to a higher rate of infection within a 5-8 day period
- **Time Frame:** 5-8 Days after placement of trial leads

- **Secondary Outcome Measure**

- **Title:** Prone fluoroscopy vs upright PA x-ray
- **Description:** Difference in lead position on prone fluoroscopy versus upright PA x-ray when comparing Dermabond plus suture versus suture only at lead insertion site
- **Time Frame:** 5-8 Days after placement of trial leads

Analytical Plan

Results will be analyzed initially using descriptive statistics. Comparison between groups will be done using chi square tests for proportions, and t-tests or ANOVA procedures for continuous variables. Regression analysis will be performed to identify independent outcome predictors. Other inferential statistical analysis will be conducted as appropriate.

Human Subjects Protection

Subject Recruitment Methods

All patients undergoing percutaneous SCS trial at Atrium Health - Wake Forest Baptist will be invited to participate in this study. All records will be kept in a secure locked location. Any electronic files will be maintained behind the medical center firewall with password protection. All information collected are de-identified without any patient specific information that can be identifiable to a particular patient.

If any collected patient identifying information corresponding to the unique study identifier will be utilized a linkage file will be stored separately from the data. The linkage file will be kept secure, with access limited to designated study personnel. Following data collection subject identifying information will be destroyed within 6 years.

Confidentiality will be protected by collecting only information needed to assess study outcomes, minimizing to the fullest extent possible the collection of any information that could directly identify subjects, and maintaining all study information in a secure manner. To help ensure subject privacy and confidentiality, only a unique study identifier will appear on the data collection form. Any collected patient identifying information corresponding to the unique study identifier will be maintained on a linkage file, store separately from the data. Data and records will be kept locked and secured, with any computer data password protected. No reference to any individual participant will appear in reports, presentations, or publications that may arise from the study.

Informed Consent

Informed consent will be obtained from all subjects prior to their participation in this research study. This evaluation will determine if it is in the subject's best interest to utilize the Dermabond plus suture or suture alone for best evaluation of the success of the lead placement for potential spinal cord stimulator placement.

Confidentiality and Privacy

Confidentiality will be protected by collecting only information needed to assess study outcomes, minimizing to the fullest extent possible the collection of any information that could directly identify subjects, and maintaining all study information in a secure manner. To help ensure subject privacy and confidentiality, only a unique study identifier will appear on the data collection form. Any collected patient identifying information corresponding to the unique study identifier will be maintained on a linkage file, store separately from the data. The linkage file will be kept secure, with access limited to designated study personnel. Following data collection subject identifying information will be destroyed within 6 years via existing confidential material destruction service at Atrium Wake Forest Baptist Medical Center consistent with data validation and study design, producing an anonymous analytical data set. Data access will be limited to study staff. Data and records will be kept locked and secured, with any computer data password protected. No reference to any individual participant will appear in reports, presentations, or publications that may arise from the study.

Data and Safety Monitoring

The principal investigator will be responsible for the overall monitoring of the data and safety of study participants. The principal investigator will be assisted by other members of the study staff.

Reporting of Unanticipated Problems, Adverse Events or Deviations

Any unanticipated problems, serious and unexpected adverse events, deviations or protocol changes will be promptly reported by the principal investigator or designated member of the research team to the IRB and sponsor or appropriate government agency if appropriate.

Risks

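### Trial length (5, 6, 7 or 8 days) is framed as a four-way comparison, and the plan does not say how it will be analysed, whether the order of the days is used, or how two leads per patient are handled

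*Combined protocol and SAP*

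**What the plan says.** Under Additional Objectives, item 3 reads "Assess trial lengths effects 5 versus 6 versus 7 versus 8 days on lead migrations rates".

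The matching secondary outcome (Outcome Measures) has a title about trial length and migration, but its description asks: "Does a longer trial predispose to a higher rate of infection within a 5-8 day period". Infection is mentioned nowhere else in the document.

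The Analytical Plan names methods in general terms: "Comparison between groups will be done using chi square tests for proportions, and t-tests or ANOVA procedures for continuous variables". It then adds: "Regression analysis will be performed to identify independent outcome predictors". Neither sentence mentions trial length. No coding of days, trend test, exact test, allowance for two leads per patient, or expected number of patients per day is given.

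Under Interventions and Interactions, each patient has one lead secured each way, with the side randomized. Each patient has one image after placement and one between days 5 and 8. A migrated lead is one that moved more than 4 mm. Nothing in the protocol assigns trial length.

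The Sample Size section covers only the comparison of securing methods.

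**The concern.** Days 5 to 8 are ordered, and the secondary outcome is worded directionally (longer trial, higher rate). If the four-way wording of Objective 3 is paired with the named tests, the result is a 4 x 2 chi-square on migration above 4 mm and a four-group ANOVA on millimetres. Both spend three degrees of freedom and give the same answer however the days are ordered.

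The within-patient design does not protect this comparison. Both leads of a patient have the same trial length, so the patient is the unit for length, and the two leads are not independent observations of it.

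Two errors are possible. A real gradient with length could be missed and reported as no effect. If leads are pooled as independent, a difference between days could be declared too readily. In addition, Objective 3 speaks of effects, although length is not randomized.

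**Working it through.** **The plan's own figure.** The inputs are "Assuming the mean lead migration for use of Dermabond is 2.49 mm compared to mean non-Dermabond usage of 3.24mm, with variance of 1mm", with "study power of 80% with 95%CI for 2-tail test is 56 for both the groups". For two independent means, n per group = 2 x (1.960 + 0.842)² x 1 / 0.75² = 27.9, so 28 per group and 56 in total. The stated figure is reproduced. The plan does not say whether 56 counts leads or patients, so I carry three readings: 28 patients as the unit, 56 leads (28 patients), and 112 leads (56 patients).

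**Expected migrated units per day.** The rate comes from Sample Size: "Lead migration is estimated to occur at a rate of about 13.2" per cent. An even split over four days is my assumption.

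| Unit | Per day | x 0.132 |
|---|---|---|
| 28 patients | 7 | 0.92 |
| 56 leads | 14 | 1.85 |
| 112 leads | 28 | 3.70 |

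In each row, 4 of the 8 cells are below 5. Reaching 5 would need 4 x 5 / 0.132 = about 152 leads.

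This depends on the rate. At 69.2%, the top of the Background range, 112 evenly split leads have no cell below 5: the smallest is 28 x 0.308 = 8.62. With 56 leads the non-migrated cells are still 14 x 0.308 = 4.31.

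**Power for millimetres.** The Background says: "Migration of the SCS leads can result in up to 2.49 mm to 3.24 mm migration in the leads depending on trial length". Spreading 3.24 - 2.49 = 0.75 mm evenly over the three steps from day 5 to day 8 gives 0.25 mm/day (assumption). I use one value per patient with SD 1 mm (assumption) and alpha 0.05. The noncentrality is n per day x the sum of squared deviations of the day means.

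- 0.25 mm/day: deviations ±0.375 and ±0.125, sum of squares 0.3125. With 14 per day it is 4.375; with 7 per day, 2.19.
- 0.4 mm/day: deviations ±0.6 and ±0.2, sum of squares 0.8. With 14 per day it is 11.2.
- Step of 0.75 mm at day 8 only, 14 per day: ANOVA 14 x 0.75² x 3/4 = 5.91; trend 14 x (1.5 x 0.75)² / 5 = 3.54.
- Step of 1.2 mm at day 8 only, 14 per day: ANOVA 14 x 1.2² x 3/4 = 15.12; trend 14 x (1.5 x 1.2)² / 5 = 9.07.

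The noncentral F distribution then gives:

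| Scenario | ANOVA (3 df) | Trend (1 df) |
|---|---|---|
| 0.25 mm/day, 28 patients | 18% | 30% |
| 0.25 mm/day, 56 patients | 36% | 54% |
| 0.4 mm/day, 56 patients | 78% | 91% |
| 0.75 mm step at day 8, 56 patients | 48% | 46% |
| 1.2 mm step at day 8, 56 patients | 90% | 84% |

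**Power for rates.** This is a simulation with 40,000 runs, independent units and an even split. The day-specific rates are assumed and average 13.2%.

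| Rates on days 5/6/7/8 | Units | Chi-square (3 df) | Trend (1 df) |
|---|---|---|---|
| 6/10/15/22% | 56 | 15% | 24% |
| 3/8/16/26% | 56 | 30% | 48% |
| 6/10/15/22% | 112 | 28% | 47% |
| 3/8/16/26% | 112 | 59% | 80% |

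With no day effect and independent units, the chi-square test rejects in 2.0% (28 units), 4.5% (56) and 4.2% (112) of runs.

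**Pooling leads as independent.** With within-patient correlation r and m leads per day, the F ratio under no effect is inflated by about (1 + r) / [(m - 1 - r)/(m - 1)]. For m = 14 this is 1.3/0.977 = 1.33 at r = 0.3 and 1.5/0.962 = 1.56 at r = 0.5. Simulating the lead-level ANOVA gives false-positive rates of about 11% and 16%, with either 28 or 56 patients. The correlations are assumed; the documents give none.

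**The case against.** The strongest reply is that the plan does not fix a four-category test. The Analytical Plan assigns no method to trial length, and the regression it lists could carry days as a numeric term. That stands. A reader might infer that the protocol commits Objective 3 to an unsound chi-square test. The documents do not support this: the gap is an unspecified method and coding, with wording that points towards four categories.

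Four further points also stand.

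- Objective 3 does not itself ask for a trend. The directional wording is in the secondary outcome, where the word is infection. With one follow-up image per patient, any slope is between patients.
- Small cells do not hold under every reading, as the 69.2% case shows. Nor do they inflate false positives here: for independent units the chi-square test is near nominal at 56 or 112, and conservative at 28.
- The advantage of a trend depends on a roughly steady gradient. For a single step it is nil or slightly reversed. The 0.25 mm/day figure is an illustration, since Sample Size uses the same 2.49 and 3.24 mm as the means for the two securing methods.
- The trend does not cure sparse events. At 56 leads, 56 x 0.132 = about 7.4 migrated leads are expected, and power for rates is 24-48% in the scenarios tried.

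These points limit the claim without removing it. Nothing in the plan secures a numeric days term or clustering by patient, and the named group tests provide neither.

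**Conclusion.** The point holds as an under-specified secondary analysis. Objective 3 is framed as a four-way comparison, the named group tests ignore order and pairing, and the listed regression is not tied to trial length.

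At the planning rate of 13.2% with an even split, a four-category table is sparse, with 0.9 to 3.7 expected migrated units per day. For a steady gradient the cost is power: 36% against 54% with 56 patients and 18% against 30% with 28, at the assumed 0.25 mm/day and SD 1 mm. If leads are pooled, the cost is a false-positive rate of about 11-16% for ANOVA on millimetres, at an assumed correlation of 0.3-0.5.

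The primary comparison of securing methods is not affected. The secondary outcome's title and description also contradict each other on migration and infection.

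**What to change.** - State in the Analytical Plan that, for Objective 3, the days between the two images enter the planned regression as one numeric term, with a patient's two leads clustered, for millimetres and for migration above 4 mm.
- Report the change per additional day with a confidence interval, as an exploratory, non-randomized, between-patient association, and reword Objective 3 to match.
- Show the four-day breakdown, with counts per day, descriptively only.
- Reconcile infection with migration in the trial-length secondary outcome.

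This costs wording only: no extra patients, visits or images. The slope assumes a roughly steady change per day, which the descriptive breakdown lets readers check. Because migration events are few, power will stay low, so an interval that includes zero should not be read as evidence that length does not matter.

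### Side is the randomized factor, but no balancing of side is described and neither side nor pairing is in the named tests: a small, avoidable loss of precision

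*Combined protocol and SAP*

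**What the plan says.** Under Interventions and Interactions, each patient has a left and a right lead, one secured each way, so that "the patient will serve as their own control". The side that gets Dermabond is set at random: "we will randomize which lead (left or right) in each patient gets suture plus Dermabond versus suture only". The stated purpose is "to limit any potential procedural (though unlikely) bias in which SCS lead gets secured in a certain fashion", and the same sentence opens by expecting no difference between sides: "Although, the anatomy of the two placement location should be identical". Blocking or other balancing of side is not mentioned. The list of subject data in that section does not name the side of each lead, although radiological information is also to be collected.

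The Analytical Plan covers the comparison in one sentence: "Comparison between groups will be done using chi square tests for proportions, and t-tests or ANOVA procedures for continuous variables". It adds that "Regression analysis will be performed to identify independent outcome predictors", with no covariates listed and no link to the primary comparison. Side is not named there as a factor, a covariate or a subgroup.

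The Sample Size section starts from "Assuming the mean lead migration for use of Dermabond is 2.49 mm compared to mean non-Dermabond usage of 3.24mm", a variance of 1, 80% power and a two-tailed test at the level implied by a 95% interval. It arrives at 56 for both groups.

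**The concern.** Side plays the part here that sequence plays in a two-period crossover: it is what is randomized, and it differs between the two treatments within every patient. If leads on one side move more than leads on the other, that difference enters every within-patient comparison, with a sign that depends on where the Dermabond went. Analysed without side, it has two linked effects. It widens the spread of the within-patient differences, and it lets a chance excess of Dermabond on one side move the estimate. Both are expressions of the same variance term, so they should not be counted twice.

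What is at stake is some power in the main comparison, and the ability to report whether the concern that the protocol itself raises turned out to matter.

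**Working it through.** **Inputs from the documents.** Means 2.49 and 3.24 mm (difference 0.75 mm), variance 1 (SD 1 mm), two-sided 5%, 80% power, total 56 (Sample Size). Two leads per patient, side randomized (Interventions and Interactions).

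**Assumed inputs, not in the documents.** Left-right difference in mean migration, delta: 0.1, 0.25 or 0.5 mm. Correlation between a patient's two leads, rho: 0 or 0.5.

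**Step 1: the plan's own figure.** For two independent groups, n per group = 2 × (1.96 + 0.84)² × 1 / 0.75² = 27.9, so 28 per group and 56 in total. The figure reproduces. Because each patient supplies one lead to each group, 56 could mean 56 leads (28 patients) or 56 patients, so both are shown.

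**Step 2: the model.** Let D be the suture-only migration minus the Dermabond-plus-suture migration in one patient, and let s be +1 or −1 according to the Dermabond side. Then D = tau + s × delta + e, with Var(e) = 2(1 − rho). If side is ignored, Var(D) = 2(1 − rho) + delta². At delta = 0.5 the added 0.25 is 12.5% of 2 (rho 0) or 25% of 1 (rho 0.5).

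**Step 3: power of the paired t-test for 0.75 mm, side ignored.** SD = √(2(1 − rho) + delta²).

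| Patients | rho | delta 0 | 0.1 mm | 0.25 mm | 0.5 mm |
|---|---|---|---|---|---|
| 28 | 0 | 77.2% | 77.0% | 75.9% | 72.3% |
| 28 | 0.5 | 96.9% | 96.7% | 96.0% | 92.8% |
| 56 | 0 | 97.4% | 97.3% | 97.0% | 95.7% |

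**Step 4: chance imbalance under simple allocation.** The 95% range of the split is 9:19 to 19:9 with 28 patients and 21:35 to 35:21 with 56. At delta = 0.5 mm the shift at those limits is (19 − 9)/28 × 0.5 = 0.18 mm, or (35 − 21)/56 × 0.5 = 0.125 mm. These are extremes at an assumed delta, and the standard error of the paired test already covers them. Simulated type I error of that test at 0.5 mm is 4.9% to 5.1%.

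**Step 5: what a side term does (28 patients).**
- *Balanced allocation.* The regression of D on s uses SD √(2(1 − rho)) with n − 2 degrees of freedom. Power is 77.1% (rho 0) or 96.8% (rho 0.5) whatever delta is. With no side effect the cost is 77.2 − 77.1 = 0.1 point at either correlation (96.9 − 96.8).
- *Simple allocation, rho 0.* The term also pays for imbalance. With no side effect, simulated power is 77.4% without it and 75.7% with it, a cost of 1.7 points. At 0.5 mm it is 72.0% without and 75.2% with, a gain of about 3 points.
- *Balanced allocation without the term.* The t-test counts side variation that the balance has already removed from the estimate, so it becomes conservative. At 0.5 mm its type I error is about 3.7% (rho 0) or 3.0% (rho 0.5).

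**Step 6: pairing, for scale.** With 28 patients, rho 0.5 and no side effect, an unpaired t-test has simulated power of 86.4% against 96.8% paired, and a type I error of 0.6% instead of 5%. Leaving pairing unstated matters more than leaving out side.

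**Step 7: the binary outcome.** If both methods had the 13.2% rate given under Sample Size and the two leads were independent, the expected number of discordant pairs would be 2 × 0.132 × 0.868 × 28 = 6.4 (12.8 with 56 patients). Positive correlation would make it smaller.

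**The case against.** The strongest reply is that the protocol expects no side difference and calls the bias unlikely. Its wording can also be read as a worry about operators choosing which lead to glue, and randomization alone answers that. This largely stands. It is why the small values of delta deserve most weight, and at 0.25 mm or less the loss is about one point.

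A reader might infer that an unmodelled side effect biases the comparison. The documents do not support that: allocation is random, so the estimate is unbiased on average and the paired test holds its level. A reader might also infer that allocation is unrestricted. The plan is silent, and silence does not show it. If the list is already balanced, the side term is still needed, for the reason in the last item of Step 5.

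Nor is the side term free in every case. Under simple allocation and correlation 0 it loses power until delta reaches about 0.3 mm. It is nearly free only when blocking goes with it.

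The power figures above assume a paired test, which the Analytical Plan does not state. With an unpaired test, 28 patients and correlation 0, a 0.5 mm side difference takes simulated power from 79.1% to 75.2%.

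Finally, the general regression sentence could be stretched to include side. It names no covariate and is not tied to the main comparison, so it answers the point only in part.

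**Conclusion.** The point holds as a minor matter of precision. Side is randomized, no balancing is described, and the named tests include neither side nor pairing. There is no failure of validity.

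The size depends on a side difference that the documents do not give. With 28 patients and correlation 0, ignoring side costs 0.2, 1.3 or 4.9 points of paired-test power at 0.1, 0.25 or 0.5 mm. With 56 patients the cost at 0.5 mm is 1.7 points. A 0.5 mm side difference would be two thirds of the planned 0.75 mm effect, which is hard to square with the protocol's expectation of identical anatomy. The case for acting is that the remedy costs almost nothing and settles the pairing question as well. Severity: consider.

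**What to change.** 1. **Allocation.** Allocate the Dermabond side in permuted blocks, so that left and right receive it equally often, and say so under Interventions and Interactions.
2. **Data.** Record the side and securing method of every lead explicitly.
3. **Main analysis in mm.** In the Analytical Plan, regress the within-patient difference (suture-only minus Dermabond plus suture) on the Dermabond side coded +1/−1. Test the intercept as the treatment effect, and report the side coefficient with its confidence interval.
4. **Outcome above 4 mm.** Use a paired analysis, such as McNemar's test. Keep a conditional logistic model with method and side as supportive only, because few discordant pairs are expected.

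Adopt items 1 and 3 together. The cost is a line in the allocation procedure, a line in the Analytical Plan, and about 0.1 point of power if there is no side effect. It needs no extra patients or imaging. If patients have already been allocated without restriction, only the side term can be added for them. At correlation 0 with 28 patients it then costs about 1.7 points if there is no side effect and gains about 3 points at 0.5 mm. Decide whether to include it before any outcome data are seen.

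### The plan accepts X-ray or fluoroscopy for the migration reading without requiring a matched baseline, so in mismatched image pairs a posture or modality difference can be recorded as migration

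*Combined protocol and SAP*

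**What the plan says.** Interventions and Interactions describes two kinds of Day 0 imaging. Fluoroscopy is used while the leads go in: "imaging is obtained during the placement of the trial leads via fluoroscopy". X-rays are then taken on Day 0 and at follow-up: "the patient will be sent for X-ray imaging right after the trial as well as between days 5-8 post procedure". The same section goes on to say that, depending on location, "the post trial images may be done via x-ray imaging or via fluoroscopy", and closes with the rule "Either radiological studies are acceptable methods to be used in the analysis of lead migration for this study". It defines the rate of migration by a cut-off of more than 4 mm.

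The Primary Outcome Measure description is narrower. It names only an X-ray pair: "comparing initial x-ray after placement versus x-ray taken at lead removal 5-8 days after placement". It does not state posture.

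Posture appears only as a separate question. Item 4 of the Additional Objectives asks whether lead position changes "when laying prone on the operating table and then standing and having a PA x-ray performed with radiology", and the last secondary outcome is "Difference in lead position on prone fluoroscopy versus upright PA x-ray when comparing Dermabond plus suture versus suture only at lead insertion site".

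The Analytical Plan lists chi-square tests, t-tests or ANOVA, and regression. It does not mention imaging modality or posture.

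**The concern.** The outcome definition and the reading rule disagree. A fluoroscopic follow-up either falls outside the X-ray-to-X-ray definition or is admitted under the permissive rule with no stated baseline. Two readers could follow the protocol, choose different Day 0 images and record different millimetres for the same lead.

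If the two images differ in posture or modality, any resulting difference in apparent lead position is added to true movement. The planned means (2.49 and 3.24 mm) lie below the 4 mm cut-off by 1.51 and 0.76 mm, so a shift of a millimetre or two would reclassify many leads. This affects the migration rate, which is the title of the primary outcome. It also affects every analysis that uses migration as an explanatory or outcome variable: against trial response, satisfaction and trial length.

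**Working it through.** **1. The plan's own figure.** Sample Size gives means of 2.49 and 3.24 mm, variance 1 (SD 1 mm), 80% power, two-sided 95%, and a total of 56.
- Difference: 3.24 − 2.49 = 0.75 mm.
- n per group = 2 × (1.96 + 0.8416)² × 1² / 0.75² = 2 × 7.849 / 0.5625 = 27.9, so 28 per group and 56 in total.

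The stated figure reproduces under an independent-groups normal approximation (power 80.1%). Matching the images does not change it.

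**2. Rates above 4 mm with matched images.** Assume migration is normal with these means and SD 1.
- Suture alone: 1 − Φ(4 − 3.24) = 1 − Φ(0.76) = 22.4%.
- Dermabond plus suture: 1 − Φ(4 − 2.49) = 1 − Φ(1.51) = 6.6%.

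**3. Rates with some mismatched pairs.** Let a fraction f of patients have mismatched images that add an apparent shift s, equal in both leads and in the direction of migration. The documents give neither f nor s. For a lead with mean m:

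rate = (1 − f) × [1 − Φ(4 − m)] + f × [1 − Φ(4 − m − s)]

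For f = 0.5 and s = 2 mm:
- Suture alone: 0.5 × 22.4% + 0.5 × 89.3% = 55.8%.
- Dermabond plus suture: 0.5 × 6.6% + 0.5 × 68.8% = 37.7%.

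| f | s (mm) | Suture alone | Dermabond + suture | Difference (points) | Ratio |
|---|---|---|---|---|---|
| 0 | – | 22.4% | 6.6% | 15.8 | 0.29 |
| 0.25 | 2 | 39.1% | 22.1% | 17.0 | 0.57 |
| 0.5 | 1 | 40.9% | 18.5% | 22.4 | 0.45 |
| 0.5 | 2 | 55.8% | 37.7% | 18.1 | 0.68 |
| 0.5 | 3 | 60.6% | 49.9% | 10.7 | 0.82 |

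The ratio moves towards 1 in every row. The difference in points first widens and then narrows, so the distortion of the risk difference has no fixed direction.

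**4. Misclassification.** At f = 0.5 and s = 2 mm, 55.8 − 22.4 = 33.4 points of the suture-alone leads are labelled as migrated only because of the shift. That is 33.4 / 55.8 = 60% of the leads so labelled. The comparisons of migrated with non-migrated patients would use these labels.

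**5. Mean difference in millimetres.** For signed displacement, (3.24 + s) − (2.49 + s) = 0.75 mm within each patient, so an equal shift cancels in a paired analysis. It does not cancel from the variance in an unpaired one: the variance becomes 1 + f(1 − f)s², which for f = 0.5 and s = 2 is 1 + 0.25 × 4 = 2. Power at 28 per group then falls from 80% to 51%. If the shift differed between securing methods by d, the paired mean difference would itself move by f × d.

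**The case against.** The strongest reply is that the primary outcome description already gives a same-modality pair, and that Interventions and Interactions also speaks of measuring from the original placement on X-ray. For a patient with both X-rays, the plan read this way needs no repair on modality. Both leads are on the same image, so they share its modality and posture, and the sample size rests on mean millimetres, where an equal shift cancels in a paired comparison. This stands, and it confines the problem to mismatched pairs and mainly to the thresholded analyses. It does not remove the permissive rule or supply the missing baseline for a fluoroscopic follow-up.

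A reader might infer more than the documents support:
- **That posture shift is counted as migration throughout.** It can enter only where the two images differ, and the documents do not say how often that happens. Applying 2 mm to every patient would give 89% vs 69%, but nothing in the plan supports so general a mismatch.
- **That the investigators expect lead position to change with posture.** Item 4 asks whether it does. The posture of a follow-up fluoroscopy image is not stated either; prone is an inference from that item and its outcome.
- **That matched Day 0 images exist for everyone, so the repair costs nothing.** The plan calls the Day 0 X-ray one taken right after the trial, and then lets post-trial images be either modality by location. If that covers Day 0, some patients have no Day 0 X-ray. Fluoroscopy is described as taken during placement, and the Dermabond lead is secured after placement, so that image may predate securing.

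**Conclusion.** The concern holds in limited form. The plan contains two unreconciled rules for the image pair and no matching requirement, so following it as written can record a posture or modality difference as migration in mismatched pairs. The exposed analyses are the rate above 4 mm and those of migration against response, satisfaction and trial length. The paired mean difference would be biased only if the shift differs by securing method, which the documents leave open.

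The size cannot be fixed from the documents. In the illustration, the rates move from 22% vs 7% to 56% vs 38%. This rests on normal migration with SD 1 mm, a 2 mm shift in half of patients, equal in both leads and always in the direction of migration. The additive model does not represent magnification, which would act as a multiplier. The absence of a named paired test in the Analytical Plan would add to the damage but is a separate matter.

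**What to change.** Reconcile Interventions and Interactions with the Primary Outcome Measure description before images are read, so that baselines are not chosen afterwards:
- Require baseline and follow-up of the same modality and posture within each patient. For an X-ray follow-up, use the Day 0 X-ray. For a fluoroscopic follow-up, use a Day 0 fluoroscopic image only if it was taken after both leads were secured, and amend the outcome description to admit this pair.
- Record modality and posture for each image.
- Use mismatched pairs only for objective 4 and for a sensitivity analysis of migration.
- State whether *post trial* images include the Day 0 image.

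The cost is a reading instruction and two short data fields. The downside is that patients without a matched pair leave the main migration analysis. Their number is unknown until the Day 0 question is settled and, because modality depends on location, they may cluster by location. The number excluded should be reported by location.
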